5.1 INCLUSION CRITERIA

A patient who meets all of the following criteria may be considered as a potential trial subject:

- 1. Male or female at least 18 years old
- 2. Subjects with minimum of 2 years life expectancy
- 3. Subjects have signed the informed consent document for data release
- 4. Subjects with infrarenal AAA who are assessed by the Investigator to be eligible for endovascular Abdominal Aortic Aneurysm Repair with the trial devices.

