5.8 FOLLOW-UP REQUIREMENTS

Subjects will be followed procedurally and to hospital discharge and at 1, 6 (standard of care follow-up; no specific trial visit is required), 12 months and annually through five years (total follow-up commitment).

Table 2 outlines a suggested follow-up schedule which may be altered to meet standard of care at individual sites.

If a subject undergoes conversion to open surgical repair, the subject will continue follow-up for 30-days post-conversion, at which point the subject will exit. If the subject has not been discharged from the conversion hospitalization within 30-days, the date of discharge will be the date of trial exit.

Table 2: Suggested Follow-Up Visit Schedule									
Suggested Schedule of Tests:	Screening/ Baseline	Procedure	Pre- Discharge	FUP 1 1 month 30 ± 15 days	FUP 2 6 Month 182± 30 days	FUP 3 1 Year 365± 60 days	>1 to 5 Years FUP (± 90 days window)		
Inclusion/Exclusion	X	-							
Demographics/Medical History	X								
Physical Exam [†]	X		X	X	X	X	X		
Blood Labs‡	X		X	X	X	X	X		
Contrast-enhanced CT scan	x [¥]			x [¥]	х*	x [¥]	х*		
Procedural Information		X							
Adverse Events		X	X	X	X	X	X		

[†]The physical exam includes overall health, physical assessment, and vital signs.

[‡]Blood labs typically include serum creatinine and hemoglobin, if collected

^{*} High resolution (<3mm slice spacing), contrast and non-contrast CT scan is preferred up to 3 months prior to the scheduled procedure *If the institution's standard of care for EVAR subjects involves another imaging modality e.g., duplex ultrasound, that modality may be collected alternatively.

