5 TRIAL EVALUATIONS

6.1 PRIMARY TRIAL ENDPOINTS

The primary trial endpoint is one -year survival in the absence of Aneurysm Related Complications (ARC). ARC is a composite of the most relevant EVAR related outcomes and includes:

- Peri-operative death (< 30-days)
- Aneurysm rupture
- Conversion to Open Surgical Repair (OSR)
- Endoleaks; post-operative
- Endograft migration (≥ 10mm)
- Aneurysm enlargement (≥ 5mm compared to 1-month CT)
- Endograft occlusion
- Reinterventions for device- or aneurysm-related complications

The outcomes above comprising of the ARC composite endpoint are defined in §12.1.

Imaging driven observations will be based on the one-year evaluation window (365 days \pm 60 days). If there are two diagnostic images available within the window, the convention will be to use any image with a positive finding.

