6.2 SECONDARY TRIAL ENDPOINTS

Secondary endpoints to be assessed up to five years include:

- 1. Major Adverse Events (MAEs) at 30-Days, 12-Months and annually thereafter, up to five years:
 - Mortality (all-cause)
 - Bowel Ischemia
 - Myocardial Infarction
 - Paraplegia
 - Renal Failure
 - Respiratory Failure
 - Stroke
 - Procedural Blood Loss ≥1,000mL
- 2. ARC post 12-Months
- 3. Individual components of ARC post 12-Months and up to five years
- 4. Aneurysm Related Mortality
- 5. Endoleaks Classified by Type
- 6. AAA Related Secondary Procedures
- 7. Device Integrity
- 8. Any adjunctive procedures necessitated during the implant procedure

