10.2 STATISTICAL METHODS

All non-imaging-driven variables in the composite endpoint will be evaluated to 1 year (day 365 post-implant), whereas imaging-driven variables will be evaluated to a 1-year window (day 365 +/- 60 days). The day of implantation will be set as day 0. Early events are defined as those occurring from the date of the procedure up to 30 calendar days post-operatively. Late events are defined as those occurring from after 30 calendar days post-operatively (from day 31 forward).

The null hypotheses for both non-inferiority and superiority will be evaluated with one-sided alpha levels of 0.05.

If the non-inferiority null hypothesis is rejected, the null hypothesis for superiority will be investigated.

Hypotheses for Non-Inferiority:

Null Hypothesis:

 $H1_0$: $\mu_A - \mu_B \le -8\%$ (AFX is inferior with respect to the primary

endpoint)

Alternative: $H1_1$: $\mu_A - \mu_B > -8\%$ (Statistical evidence of non-inferiority)

Hypotheses for Superiority:

Null Hypothesis: $H2_0: \mu_A - \mu_B \le 0$ (The two device groups have equal effect)

Alternative: $H2_1$: $\mu_A - \mu_B > 0$ (Statistical evidence of superiority)

Data for the primary endpoint will be presented as point estimates for both the treatment (AFX device) and control (proximally fixated devices), along with a 95% confidence interval for the difference. The lower bound of a one sided 95% confidence interval is used to evaluate the non-inferiority and superiority null hypotheses.

Quantitative parameters will be described using the following summary descriptive statistics: number of non-missing values, mean, standard deviation, median, first and third quartiles, and minimum and maximum values.

Qualitative parameters will be described overall using frequencies and percentages. Percentages will be calculated on the number of non-missing observations. In all cases, the number of missing values will be specified.

Kaplan-Meier estimates will be generated for the composite endpoint components across the duration of the trial.

Sample Size Determination:

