12 DEFINITIONS

12.1 DEFINITIONS ASSOCIATED WITH THE COMPOSITE PRIMARY ENDPOINT ARC

The primary trial endpoint is an assessment at one year, where survival is in the absence of Aneurysm Related Complications (ARC). ARC is a composite of the most relevant EVAR related outcomes and include:

- *Aneurysm Rupture*: bleeding or leaking of blood from the aneurysm subsequent to the index procedure.
- Conversion to Open Surgical Repair (OSR): open surgical repair of the abdominal aortic aneurysm due to unsuccessful delivery or deployment of the stent graft, due to complications or other clinical situations that precluded successful endovascular treatment, or at any time following initial successful endovascular treatment for any reason. Excludes post-mortem explant of the trial device.
- Endoleaks: clear evidence of contrast within the aneurysm sac
 - **Endoleak Type Ia** Contrast material in the aneurysm sac adjacent to the proximal seal zone and/or between the endograft and the inner wall of the proximal attachment site.
 - **Endoleak Type Ib** Contrast material in the aneurysm sac adjacent to the distal seal zone and/or between the endograft and the inner wall of the distal attachment site.
 - **Endoleak Type II** Contrast material along the posterior sac wall with visualization of lumbar artery or the inferior mesenteric artery

LEOPARD AAA US Post-Market Trial

- Endoleak Type IIIa Component disconnect
- Endoleak Type IIIb Mid-graft hole
- *Migration* (≥10mm): stent distal movement ≥10mm from the original implant location relative to the center of the distal renal artery; as compared to the 1-month CT scan location.
- Aneurysm Sac Enlargement: aneurysm sac diameter increase of ≥5mm in late followup as compared to 1-month CT scan location.
- *Endograft Limb Occlusions*: defined as total obstruction of blood within the lumen of a device limb irrespective of whether a secondary intervention is necessary.
- *Endograft Stenosis:* defined as a reduction in lumen >50% by, for example, thrombus, intimal hyperplasia, or endograft kink/twist.

Elaboration of the above definitions can be found in the Adjudication Charter.

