12.3 MAJOR ADVERSE EVENT

An event occurring during the trial that meets one of the following criteria:

- *All-Cause Mortality*:
- Death is defined as any death occurring during the trial period, regardless of cause.
 - O Aneurysm-related death: is defined as any death occurring within 30-days from the date of the index procedure, regardless of cause, and death due to aneurysm rupture or death within 30-days of any secondary procedure intended to treat the aneurysm.
 - o Cardiac-related death: is defined as death due to arrhythmia, heart failure (including cardiogenic shock), or myocardial infarction
 - o *Pulmonary-related death:* is defined as death due to due to pulmonary edema, respiratory failure, or pulmonary embolism
 - Vascular-related death: is defined as death due to stroke, cerebral hemorrhage, or other clear vascular event that is not categorized as cardiac-related or pulmonary-related or aneurysm-related.
 - o *Other:* is to be used to identify a death due to any event that cannot be clearly categorized as above, but where some information is available.
 - o *Unknown*: is to be used to identify a death where no information is available.
- *Bowel Ischemia:* the lack of adequate blood flow to the intestines that requires intensification of medical therapy or surgical/endovascular intervention.

- Myocardial Infarction: increase of one or more cardiac biomarkers (preferably troponin) with at least one value above the 99th percentile of the upper reference limit (URL) together with evidence of myocardial ischemia with at least one of the following: myocardial ischemia; ECG changes indicative to new ischemia (new ST-T changes or left bundle branch block (LBBB)); development of pathological Q-waves in the ECG; imaging evidence of new loss of viable myocardium or new regional wall motion abnormality.
- Paraplegia: paralysis of the lower extremities inclusive of the lower trunk;
- Renal Failure permanent dialysis dependence or kidney transplant
- Respiratory Failure: respiratory failure requiring ventilator support beyond 24 hours post-procedure
- *Stroke:* a sudden development of neurological deficit due to vascular lesions of the brain such as hemorrhage, embolism, or thrombosis that persists for >24 hours;
- *Index Procedural Blood Loss* >1,000mL: estimated blood loss during the index procedure ≥1,000mL.

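### Kaplan-Meier is planned for the individual ARC components with no stated rule for death or conversion; under standard censoring, 1-KM read as absolute risk overstates five-year component risk

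*Combined protocol and SAP*

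**What the plan says.** Section 10.2 names one time-to-event method: "Kaplan-Meier estimates will be generated for the composite endpoint components across the duration of the trial". Section 6.2 lists as a secondary endpoint "Individual components of ARC post 12-Months and up to five years". Section 5.8 sets visits at "12 months and annually through five years (total follow-up commitment").

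Two kinds of event can remove a patient from risk in these curves.

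- **Death.** The only death in the composite (section 6.1) is peri-operative. Later death is recorded as a major adverse event under section 12.3: "Death is defined as any death occurring during the trial period, regardless of cause".
- **Conversion to open repair.** This is an ARC component and counts "at any time following initial successful endovascular treatment for any reason" (section 12.1). After it, "the subject will continue follow-up for 30-days post-conversion, at which point the subject will exit" (section 5.8), or at hospital discharge if that is later.

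Section 10.2.2 says only that missing values are not replaced. No section gives a censoring rule for the component curves or names a competing-risk method. Section 10.1 points to a statistical analysis plan for further detail; no separate SAP text is in the document reviewed.

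**The concern.** A patient who has died cannot go on to have an endoleak, migration, sac enlargement, limb occlusion, rupture, conversion or reintervention. A patient whose graft has been replaced by open repair can no longer have the graft-dependent ones. If such patients are censored, Kaplan-Meier treats them as though they still carried the same future risk as those under observation. One minus the curve then describes a population in which nobody dies or converts.

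Deaths within five years are foreseeable, because entry asks only for "Subjects with minimum of 2 years life expectancy" (section 5.1). At stake are the absolute long-term component risks. Section 4.2 says that the trial is to evaluate outcomes in a real-world population and to be a reference for later work, and for that purpose absolute risks should allow for patients who die.

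**Working it through.** **Nothing to reproduce.** The documents state no component rate, mortality rate or Kaplan-Meier figure for five years. The check shows the direction of the bias and its size over assumed ranges.

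**Inputs from the documents.** Horizon T = 5 years (section 5.8); late death outside the composite (section 6.1); exit after conversion (section 5.8).

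**Assumed inputs.** Five-year mortality m = 10-40%; five-year conversion v = 0-5%; five-year component 1-KM value k = 1-30%; constant, independent hazards.

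**Formulas.**
- Component hazard: h_c = -ln(1-k)/T. Death: h_d = -ln(1-m)/T. Conversion: h_v = -ln(1-v)/T.
- Total hazard: H = h_c + h_d + h_v.
- Cumulative incidence (the Aalen-Johansen target): CIF = (h_c/H) × (1 - exp(-H·T)).
- Relative overstatement: k/CIF - 1.

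**Worked case: k = 20%, m = 30%, v = 0.** h_c·T = -ln(0.80) = 0.2231. h_d·T = -ln(0.70) = 0.3567. The sum is 0.5798, and exp(-0.5798) = 0.80 × 0.70 = 0.56. CIF = (0.2231/0.5798) × 0.44 = 16.9%. The excess is 3.1 points, or 18% relative.

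**Results.** Each cell gives CIF, with the relative overstatement by 1-KM in brackets.

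| 1-KM at 5 years | Conversion | m = 10% | m = 20% | m = 30% | m = 40% |
|---|---|---|---|---|---|
| 1% | 0% | 0.95% (5.4%) | 0.90% (11.6%) | 0.84% (18.9%) | 0.78% (27.7%) |
| 1% | 5% | 0.93% (8.0%) | 0.87% (14.3%) | 0.82% (21.7%) | 0.77% (30.7%) |
| 10% | 0% | 9.50% (5.3%) | 8.98% (11.4%) | 8.44% (18.5%) | 7.87% (27.1%) |
| 10% | 5% | 9.27% (7.9%) | 8.77% (14.1%) | 8.24% (21.3%) | 7.69% (30.1%) |
| 20% | 0% | 19.02% (5.2%) | 18.00% (11.1%) | 16.93% (18.1%) | 15.81% (26.5%) |
| 20% | 5% | 18.57% (7.7%) | 17.58% (13.8%) | 16.55% (20.9%) | 15.46% (29.4%) |
| 30% | 0% | 28.56% (5.0%) | 27.07% (10.8%) | 25.50% (17.6%) | 23.85% (25.8%) |
| 30% | 5% | 27.90% (7.5%) | 26.45% (13.4%) | 24.93% (20.3%) | 23.33% (28.6%) |

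**Range.** The relative excess runs from 5.0% to 30.7%. In points it runs from 0.05 (k = 1%, m = 10%, v = 0) to 6.7 (k = 30%, m = 40%, v = 5%). For a 1% component it never exceeds 0.23 points.

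**What drives it.** At k = 10% and v = 0, raising mortality from 10% to 40% moves the relative excess from 5.3% to 27.1%. At k = 10% and m = 30%, raising conversion from 0 to 2% to 5% moves it only from 18.5% to 19.6% to 21.3%.

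**At one year.** With k = 5-20% and one-year mortality of 3-10% (assumed), the excess is 1.5-5.3% relative, or 0.07-1.0 points.

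**Simulation check.** With 228 patients per arm, 10% dropout per year, 30% mortality, 3% conversion and 400 runs, 1-KM gave 20.0% against 16.7% by Aalen-Johansen.

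**The case against.** The strongest reply is that the plan never says that death or conversion is censored. Section 10.2 has a single sentence on Kaplan-Meier, and the rule may stand in the SAP that section 10.1 cites. A reader might infer that the plan expressly adopts the wrong censoring rule; the documents do not support that. What they show is a named estimator with no rule, and the bias follows if standard practice is applied. If death were instead counted as a failure, the curve would no longer measure the component's own risk. A written rule is needed either way.

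Second, section 10.2 also provides for frequencies and percentages, and it does not tie Kaplan-Meier to the secondary endpoint on individual components. The curves could be a descriptive display. That stands, so one cannot say that the plan fixes 1-KM as the estimator of that endpoint. They remain the only time-to-event summary named for the components.

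Third, a curve that censors death can be defended as a description of durability among patients still alive with the graft. It misleads only when read as absolute patient risk. That is why the point is confined to that reading, but it is the natural reading in a trial meant to describe real-world outcomes.

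Fourth, the excess is modest beside sampling error. With 455/2 ≈ 228 per arm, the 95% half-width around 20% is 1.96 × √(0.2 × 0.8/228) ≈ 5 points before attrition, against an excess of 2.0-4.2 points at 20-40% mortality without conversion. This limits the practical weight, but more patients would not remove the bias.

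A reader might also infer that the comparison between arms is distorted. Nothing in the documents suggests that mortality or conversion differs by arm. If they are similar, both arms shift by a similar amount.

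**Conclusion.** The point holds in a limited form. The plan names Kaplan-Meier for the individual components over five years and gives no rule for death or conversion. If these events are censored, 1-KM read as absolute risk is too high for the non-fatal components and for rupture. The direction is certain whenever such events occur. The size depends on rates that the documents do not give: about 5-31% relative under the assumed mortality of 10-40% and conversion of 0-5%, mainly from death, and negligible in points for rare components.

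The point does not reach every component equally. The curve for peri-operative death is unaffected, and for conversion itself only death competes. It also does not reach the primary non-inferiority and superiority tests, which section 10.2 bases on a confidence bound for the one-year difference and not on these curves. It should be corrected, but no decision rule of the trial depends on it.

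**What to change.** Replace the Kaplan-Meier sentence in section 10.2 with:

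> Cumulative incidence (Aalen-Johansen) of each ARC component other than peri-operative death will be estimated to 5 years by arm, with death, and for graft-dependent components conversion to open repair, as competing events.

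List which components count as graft-dependent. Kaplan-Meier may be used where death is itself an event, such as all-cause mortality or freedom from death or ARC. The text reviewed does not plan those curves, so they would be additions. If the SAP already contains a rule, section 10.2 should state it and agree with it.

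The cost is one sentence and a little more analysis work. Deaths and conversions are already collected (sections 12.3 and 12.1), so no new data are needed. The downside is that reported component risks become slightly lower.

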Secondary Endpoints	 MAEs at 30-Days, 12 Months and Annually ARC Post 12 Months up to Five Years Aneurysm Related Mortality Endoleaks Classified by Type AAA Related Secondary Procedures up to Five Years Device integrity Any adjunctive procedures necessitated during the implant procedure 					
Additional Evaluations	 Total Endovascular time; from catheter introduction to catheter removal Anaesthesia Time Fluoroscopy Time Contrast Volume used Total Procedure Time; from cut-down to closure Time in ICU Total Radiation Exposure Additional Imaging 					

Statistical Considerations

The primary endpoint will be evaluated in both the AFX and proximally fixated device groups. The relative performance of the two groups will be evaluated through one-sided tests for non-inferiority and superiority. Combining the superiority and non-inferiority trials into a single closed testing procedure allows for maintenance of a controlled Type 1 error rate. An 8% margin will be used for the non-inferiority test. If the non-inferiority null hypothesis is rejected, the null hypothesis for superiority will be investigated.

Hypotheses for Non-Inferiority:

Null Hypothesis: $H1_0$: $\mu_A - \mu_B \le -8\%$ (AFX is inferior with respect to the

primary endpoint)

Alternative: $H1_1: \mu_A - \mu_B > -8\%$ (Statistical evidence of non-

inferiority)

Hypotheses for Superiority:

Null Hypothesis: $H2_0$: $\mu_A - \mu_B \le 0$ (The two device groups have equal effect)

Alternative: $H2_1$: $\mu_A - \mu_B > 0$ (Statistical evidence of superiority)

The original trial size was selected to provide 80% power for the superiority test. The original sample size required, for non-inferiority testing, is relatively smaller; thus, the power of the non-inferiority test approaches 100% with the revised sample size.

Suggested Schedule of Tests

Patient eligibility will be assessed by the Investigator per institutional standard of care pre-procedural imaging. Blood work and physical exam will also be collected as per routine schedule at each institution.

Following Institutional Review board approval and patient written informed consent, the patient will be screened for eligibility. Subjects will be followed procedurally and to hospital discharge and per institutional standard of care thereafter through to 5 years (total follow-up commitment).

Table 1 outlines a typical site follow-up schedule which will be altered to meet standard of care at individual sites.

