Given an alpha error rate of 0.05, a desired power of 90%, and assuming a success rate (in terms of the primary endpoint) of 86% for AFX with an 8% advantage over the control group, the sample size required to demonstrate non-inferiority is 154 subjects in total. In order to have enough power to evaluate all hypotheses the sample size for this trial was driven by the evaluation of superiority. In this case, an alpha error rate of 0.05, power of 80%, success rate of 86% for AFX, and a relative 8% advantage in AFX's favor requires 566 patients. A 7% advantage in AFX's favor requires 724 patients. An approximate dropout rate of 10%/1-year indicates 804 patients should be enrolled to provide 724 patients at 1 year. The original protocol thus called for enrollment of up to 800 subjects. The enrollment was completed at 455 subjects after an unplanned analysis supported that the superiority evaluation was futile. With a total of 455 subjects enrolled, 410 are assumed to reach the 1-year endpoint after 10% dropout. This sample size results in 99% power for the non-inferiority test under original assumptions, and thus the trial is considered adequately powered for evaluating non-inferiority. The sample size has been determined with PASS version 12.0.2.

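### Section 10.2: 154 subjects do not give 90% power for non-inferiority; the plan's own inputs require 196, and 154 gives about 83%

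*Combined protocol and SAP*

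**What the plan says.** The sample size paragraph of section 10.2 starts with non-inferiority. It takes alpha 0.05, 90% power and a "success rate (in terms of the primary endpoint) of 86% for AFX with an 8% advantage over the control group", and concludes that "the sample size required to demonstrate non-inferiority is 154 subjects in total".

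That sentence gives neither the margin nor the sidedness. Both are set elsewhere:

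- Section 10.2, before the hypotheses: "The null hypotheses for both non-inferiority and superiority will be evaluated with one-sided alpha levels of 0.05".
- Synopsis (section 3), Statistical Considerations: "An 8% margin will be used for the non-inferiority test". The hypotheses in the synopsis and in section 10.2 put this margin on the difference in success rates.
- Section 4.5: allocation is 1:1.

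The same paragraph gives two superiority sizes at 80% power. For the first, "a relative 8% advantage in AFX's favor requires 566 patients"; for the second, a 7% advantage needs 724. It then reports that enrolment closed at 455, assumes 410 reach one year, and states: "This sample size results in 99% power for the non-inferiority test under original assumptions".

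**The concern.** The paragraph holds four checkable results: 154, 566, 724 and 99% power at 410. Three agree with one another under a single set of inputs, and 154 does not. It is too small for 90% power at the margin and alpha that the plan sets.

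Two things are at stake. A reader cannot reproduce the only required size that the plan gives for non-inferiority. That matters more after Revision 02, whose stated reason for changing section 10.2 is that the size should now be judged for non-inferiority. Also, if 154 is a correct output of some other calculation, then a margin, alpha or power different from those in the hypotheses was used at some stage, and the plan should say so.

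**Working it through.** **Inputs**

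| Input | Value | Source |
|---|---|---|
| Alpha | 0.05, one-sided | Section 10.2 |
| Margin | 8 points on the difference | Synopsis; section 10.2 hypotheses |
| AFX success rate | 86% | Section 10.2 |
| Control success rate | 86 − 8 = 78% (79% for a 7-point advantage) | Section 10.2 |
| Power | 90% non-inferiority, 80% superiority | Section 10.2 |
| Allocation | 1:1 | Section 4.5 |

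**Formula** (unpooled normal approximation, each arm rounded up):

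n per arm = (z_alpha + z_beta)² × [pA(1 − pA) + pB(1 − pB)] / (pA − pB + margin)²

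**Step 1: reproduce the plan's superiority sizes** (margin 0, 80% power).

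- 86% vs 78%: n = 282.08, so 283 per arm and 566 in total. The plan says 566.
- 86% vs 79%: n = 361.24, so 362 per arm and 724 in total. The plan says 724.

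Both match exactly, which fixes the reading of alpha, sidedness and the absolute scale.

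**Step 2: apply the same formula to non-inferiority** (margin 0.08, 90% power).

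n = (1.645 + 1.282)² × (0.1204 + 0.1716) / 0.16² = 97.68, so 98 per arm and **196 in total**. The plan says 154. The gap is 196 − 154 = 42, and 42/196 = 21%.

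**Step 3: power at given sizes.**

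Power = Φ( 0.16 / √(0.292/n) − 1.645 )

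| Total (per arm) | Normal approximation | Exact binomial enumeration of the same test | Plan |
|---|---|---|---|
| 154 (77) | 83.0% | 83.4% | 90% |
| 196 (98) | 90.1% | 90.5% | not given |
| 410 (205) | 99.5% | 99.5% | 99% |

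**Step 4: look for another route to 154.** Totals at one-sided 0.05 and 90% power, unless noted:

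- Pooled variance 198; Farrington-Manning 202; continuity-corrected 222; arcsine 224.
- Margin expressed as a risk ratio, 180 to 304; as an odds ratio, 260 to 314.
- Relative 8% advantage, 222 to 264; 7-point advantage, 218 to 244.
- 86% read as the control rate (AFX 94%), 120 to 144.
- Power 80% instead of 90%, 142 to 168 across methods (142, 144, 148, 168), none of them 154.
- One-sided 0.025 instead of 0.05, 240 to 266.

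Dropout cannot explain the gap. Inflation raises the number, and 154 is already below the uninflated 196 (218 after allowing for 10% loss). Totals at or close to 154 appear only when a stated input is changed: one-sided alpha 0.10 (150 unpooled, 154 Farrington-Manning), a 10-point margin (156), or a 7-point advantage at 80% power (158). The documents support none of these as the source.

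**Step 5: the word *relative*.** A relative 8% advantage would put control at 86/1.08 = 79.6% (862 in total) or 0.92 × 86 = 79.1% (748 in total). Only an absolute 8 points gives 566.

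**The case against.** The strongest objection is that nothing depends on 154. Section 10.2 says that superiority drove the size. Enrolment has closed, and adequacy is argued from 99% power at 410, which reproduces. This stands, and it limits the finding to a correction of the record.

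A second objection is that 196 depends on the test. The plan names PASS 12.0.2 but no procedure, and other standard methods for the difference in proportions give 198 to 222. This stands in part: 196 belongs to the formula that matches the plan's other two sizes exactly, and that the same procedure was used for non-inferiority is an inference. The alternatives all lie further from 154, so they do not rescue it.

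Third, the sentence with 154 does not itself state margin or sidedness, and section 10.1 refers to the SAP for further detail. The figure could be a correct result from inputs not shown here, in which case putting in 196 would hide the cause. That is a fair reason to let the sponsor disclose the inputs instead. It does not make 154 consistent with the margin and alpha that the plan states.

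**Conclusion.** The figure of 154 is wrong as written. On the plan's stated inputs the non-inferiority requirement at 90% power is 196 evaluable subjects, and 154 gives about 83%. The understatement is 42 subjects (21%), with a type II error of about 17% against the 10% implied. The conclusion rests on one-sided alpha 0.05, the absolute 8-point margin, 86% versus 78%, equal allocation, and the formula that returns 566 and 724. That 154 does not reproduce is secure under every standard method tried; the exact replacement value depends on the method. The origin of 154 cannot be determined from the documents.

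The error does not touch enrolment, the analysis or the 99% power statement at 410. Agreement on that last figure confirms only its arithmetic under the assumed 8-point advantage. Whether that advantage was still a reasonable assumption once superiority had been judged futile is a separate question.

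**What to change.** In the sample size paragraph of section 10.2, do one of the following:

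- replace 154 with 196 evaluable subjects (98 per arm), naming the test, the one-sided alpha of 0.05 and the 8-point margin in the same sentence; or
- state the inputs and PASS procedure that produced 154, and confirm that the 8-point margin and one-sided 0.05 govern the analysis.

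In the superiority sentence, describe the 8% as an absolute difference in percentage points.

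The cost is one number (or one sentence of inputs) and one phrase. Conduct, enrolment and analysis do not change.
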